	Visit 1 (Screening [Day -28 to -1]) b	Visit 2 (Baseline [Day 1])	Visit 3 (Week 4 [±1 wk])	Visit 4 (Week 8 c [±1 wk])	Visit 5 (Week 14 [±2 wks])	Visit 6 (Week 24 [±2 wks])	Visit 7 (Week 36 [±2 wks])	Visit 8 (Week 48 [±2 wks])	ET Visit	Visit 9 d (Week 60/ [±4 wks] EOT or Rollover to Extension)							
Muscle strength by quantitative dynamometry with hand-held device	X		X		X	X		X	X	X							
Muscle strength by quantitative dynamometry with bed frame equipment	X		X							X							
MFM domain 1	X			X		X		X	X	X							
FSHD-RODS	X		X			X			X	X							
FSHD-HI	X		X			X			X	X							
PGIC					X	X	X	X	X	X							
6-MWT	X		X	X	X	X	X	X	X	X							
Spirometry		X				X		X	X	X							
Losmapimod dispensing				Study Drug will be dispensed starting at Visit 4. Resupply will be provided as needed throughout the study, until EOT													
Outpatient Mobility Assessment		Intermittently from Visit 2 to End of Study															
AE Monitoring		Continuous from signing of ICF to End of Study															
Medications review		Continuous from signing of ICF to End of Study															

a. Unscheduled visits can be scheduled at the discretion of the principal investigator to perform any assessments related to any AEs/SAEs that arise.

b. Subjects are required to fast for at least 4 hours prior to the screening visit.

c. Visit 4 is the end of the pre-treatment period and the beginning of the treatment period. Dosing will begin at Visit 4.

d. Any visit can be split into 2 days with overnight hotel stay as needed to accommodate performance of MRI and US, or to accommodate busy site schedules.

- e. Specific questions about FSHD history will be included in the baseline medical history exam.
- f. Height will be measured at screening only
- g. A full physical examination, including a neurological examination, will be performed at Screening. Symptom-directed physical examinations and laboratory assessments can be performed at any time at the discretion of the investigator.
- h. Vital sign measurements will be performed after subjects have rested for at least 5 minutes.
- i. Standard 12-lead ECGs will be performed after the subject has been supine for at least 5 minutes. ECGs will be collected at screening, before dosing only at Visit 4, and at approximately 3 hours ( $\pm$  90 minutes) after dosing for all other on-treatment visits.

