### **Adverse Events**

AEs will be coded using the Medical Dictionary for Regulatory Activities (MedDRA). The overall incidence of AEs will be summarised by MedDRA primary System Organ Class (SOC) and Preferred Term (PT).

All AEs will be displayed in listings or graphs when appropriate. In addition, SAEs and treatment-emergent AEs (TEAEs) leading to discontinuation of study drug will be listed.

A TEAE is defined as an AE observed after starting administration of the specific treatment. If a subject does experience an event both prior to and after starting administration of a treatment, the event will be considered a TEAE (of the treatment) only if it has worsened in severity (ie, it is reported with a new start date) after starting administration of the specific treatment and prior to the start of another treatment.

The number of TEAEs and the number of subjects with at least 1 TEAE will be summarised for the following:

- SOC and PT;
- SOC, PT, and maximum severity;
- SOC, PT, and maximum drug relatedness.

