## 1.4 EXTENSION ENDPOINT

### 1.4.1 Primary Endpoint

The primary endpoint is the safety and tolerability based on AEs, clinical laboratory test results, ECGs, and vital signs.

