### 2.2 DEFINITIONS OF ANALYSIS SETS

There is only one analysis set for the study, i.e. safety analysis set, which is defined as subjects who received at least one dose of losmapimod.

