#### 3.1.1 Disposition of Subjects

The number of subjects screened and the number (percent) of subjects who failed screening will be summarized.

Study Completion: The number (percent) of treated subjects who completed the study (Week 60) and who discontinued from the study will be summarized according to the reasons for discontinuation.

Entered Study Extension: The number (percent) of treated subjects who entered the extension of the study.

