### 3.2.2 Adverse Events (AEs)

The AE verbatim descriptions (investigator terms from the case report forms [CRF]) will be classified into medical terminology using the Medical Dictionary for Regulatory Activities (MedDRA). AEs will be coded to primary System Organ Class (SOC) and preferred term (PT) using MedDRA, version 23.0.

A TEAE is defined as an AE that meets any of the following conditions:

- begins on or after the first dose of study drug and before the stop of study drug + 7 days;
- begins before the first dose of study drug and worsens on or after the first dose of study drug and before the stop of study drug + 7 days;
- is completely missing an onset date and an end date;

- is completely missing an onset date and the end date is on or after the first dose of study drug.

Only those AEs that are treatment emergent will be included in summary tables. All AEs, treatment emergent or otherwise, will be presented in subject data listings.

In summary tables, the incidence of TEAEs will be reported as the number of subjects and their percentages with TEAEs within SOC and PT. Subjects will be counted only once within a SOC and PT, even if the subject experienced more than one TEAE within a specific SOC and PT. The number of subjects and their percentages with TEAEs will also be summarized by maximum severity (mild, moderate, or severe) (or by highest common terminology criteria for AEs [CTCAE] grade).

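### The AE tables pool the main study and the extension into one ever-affected percentage, so the AE part of each primary safety endpoint cannot be read on its own

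*SAP*

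**What the plan says.** SAP 1.3.1 gives the main study a primary endpoint of safety and tolerability that includes AEs and SAEs. SAP 1.4.1 gives the extension its own: "The primary endpoint is the safety and tolerability based on AEs, clinical laboratory test results, ECGs, and vital signs".

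The AE analysis does not follow that division.

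- **Analysis set (SAP 2.2):** "There is only one analysis set for the study, i.e. safety analysis set", meaning everyone who took at least one dose.
- **Window (SAP 3.2.2):** an event is treatment-emergent if it "begins on or after the first dose of study drug and before the stop of study drug + 7 days". Worsening of an earlier event is judged over the same window. Roll-over is not a boundary.
- **Measure (SAP 3.2.2):** "the incidence of TEAEs will be reported as the number of subjects and their percentages with TEAEs within SOC and PT", with each subject counted once per SOC and PT.
- **Other AE tables (SAP 3.2.2 and 3.2.2.1):** severity, death, SAE, discontinuation and relatedness tables all report numbers and percentages of subjects with treatment-emergent events, so they share that window.
- **Pre-dose events:** "Only those AEs that are treatment emergent will be included in summary tables". Earlier events appear only in listings, although protocol Table 2 has AE monitoring "Continuous from signing of ICF to End of Study".

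Protocol 10.2.3 has no period split either. It does plan both the number of treatment-emergent AEs (TEAEs) and the number of subjects with at least one. The SAP keeps only the subjects.

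Elsewhere the SAP recognises the two parts. Section 3.1.6 defines compliance separately for each, and section 3.1.1 has "Entered Study Extension: The number (percent) of treated subjects who entered the extension of the study".

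**The concern.** Two primary endpoints with an AE component need two AE summaries, or at least one that can be taken apart. A subject counted once over the whole treatment period may have had the event in the first year, in the extension, or in both, and the table does not show which. The denominator does not suit the extension either: protocol inclusion criterion 10 admits only subjects who completed the Week 60 visit, while the SAP percentage is taken over all treated subjects.

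The extension is also where most of the exposure can lie. The protocol (section 6.5) describes earlier treatment lasting up to 52 weeks, and the analysis windows in SAP Table 1 run far beyond that. Alternate extension contacts are telephone calls and extension ECGs are at the investigator's discretion (protocol Table 3), so AEs carry much of the extension endpoint.

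**Working it through.** **Inputs.** Dosing starts at protocol Week 8 (Visit 4) and the main study's treatment ends at Week 60 (protocol Table 2). The last window in SAP Table 1 is protocol Week 276. Enrolment closed at 14 subjects (protocol 4.4). Neither document gives an AE rate, and the sample size has no statistical basis, so there is no planned AE figure to reproduce. The timings can be checked.

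**Step 1: timings.**
- Main study: 60 − 8 = 52 weeks on drug, as protocol 3.1.5 states.
- Last window: 276 − 8 = 268 weeks, and 268 × 7 = Day 1876, as in SAP Table 1.
- Extension up to that window: 268 − 52 = 216 weeks, which is 216/268 = 81% of the time on drug and 216/52 = 4.2 times the main study.

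**Step 2: effect of follow-up alone.** Assume a constant first-event rate r, no dropout, and everyone followed to Week 276. The percent ever affected is 1 − exp(−r × t), with t = weeks × 7/365.25. This gives t = 0.997 years for 52 weeks, 4.140 for 216 and 5.136 for 268.

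| Assumed r per subject-year | Main, 52 weeks | Extension alone, 216 weeks | Pooled, 268 weeks |
|---|---|---|---|
| 0.05 | 4.9% | 18.7% | 22.6% |
| 0.10 | 9.5% | 33.9% | 40.2% |
| 0.20 | 18.1% | 56.3% | 64.2% |
| 0.50 | 39.2% | 87.4% | 92.3% |

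Risk is the same throughout each row. The pooled figure differs from the main-study figure only because of time. The extension column shows that percentages by period would not be enough: they differ because the periods differ in length. A rate per subject-year is needed.

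**Step 3: what the pooled figure can identify.** Suppose 7 of 14 subjects (50%) are counted for some preferred term. With one count per subject, this fits 7 affected in the main study and none in the extension, none and then 7, or the same 7 in both. The planned table is identical in all three cases.

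**Step 4: how precise period results would be.** If all 14 roll over and stay to Week 276, exposure is 14 × 0.997 = 14.0 subject-years in the main study and 14 × 4.140 = 58.0 in the extension. At event rates of 0.10 and 0.20 this means 1.4 and 2.8 expected events, then 5.8 and 11.6. If none of 14 subjects is affected, the two-sided 95% upper limit is 1 − 0.025^(1/14) = 23.2%. Period results would be descriptive only.

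**Step 5: the pre-dose period.** Eight weeks gives 14 × 8/52.18 = 2.1 subject-years. Adding up to four weeks of screening gives 14 × 12/52.18 = 3.2.

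**The case against.** The strongest reply is that nothing is lost. All AEs are listed by subject, SAP 2.3.2 uses study day to show when events start and stop, and time on treatment is summarised. With 14 subjects a reader can place each dated event in a period by hand. A cumulative table is a legitimate summary for an untested, descriptive pilot, and protocol 10.2.3 requires no period split. The 268 weeks is the last analysis window rather than a planned duration, and the rates above are assumptions. All of this stands, and it limits the point to what is tabulated. Sorting listings by hand is still not a planned summary of a primary endpoint.

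A reader might infer four stronger things that the documents do not support.

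- **That neither safety endpoint gets an interpretable answer.** AEs are one component. Laboratory values (SAP 3.2.3), vital signs (3.2.4.1) and ECG interpretation shifts (3.2.4.3) are summarised by visit and can be assigned to a period.
- **That leaving pre-dose AEs out of the tables is a serious fault or a clear breach of the protocol.** No objective asks for that comparison, and 2.1 to 3.2 subject-years is a weak reference. Protocol 10.2.3 does say "The overall incidence of AEs will be summarised by MedDRA primary System Organ Class (SOC) and Preferred Term (PT", but it then sends all AEs to listings or graphs and specifies its detailed tables for TEAEs, so a conflict is arguable at most.
- **That the extension must show whether AEs become more frequent with time.** Its objective is the safety and tolerability of long-term dosing, worded almost as in the main study.
- **That extension withdrawals go unreported.** SAP 3.1.1 ties completion to Week 60 but does not limit discontinuations by reason to the main study. The text is unclear rather than silent.

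**Conclusion.** The point holds for the AE tables. Following SAP 3.2.2 and 3.2.2.1 as written gives percentages that cannot be attributed to either the main-study or the extension endpoint and that rise with follow-up alone. At assumed constant rates of 0.10 and 0.20 per subject-year, with no dropout and follow-up to protocol Week 276, the rise from 52 to 268 weeks is from 9.5% to 40% and from 18% to 64%. Its actual size depends on how long each subject stays in the extension and on AE rates that the documents do not give. The lack of a split, of an extension denominator and of any exposure-based rate rests on the text alone. So does the omission of the TEAE count in protocol 10.2.3.

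This is a worthwhile, inexpensive improvement to a primary analysis. It does not undermine the safety evaluation as a whole.

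**What to change.** Keep the overall tables. In SAP 3.2.2 and 3.2.2.1 add tables of TEAEs, SAEs and AEs leading to discontinuation of treatment for two periods:

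- **Main study:** first dose to the actual roll-over date, or to stop of drug + 7 days for subjects who do not roll over. The denominator is all treated subjects. This keeps events in the week after the last dose for subjects who finish at Week 60.
- **Extension:** roll-over date to stop of drug + 7 days. The denominator is subjects who rolled over.

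In each, give the number of events (which also restores the count in protocol 10.2.3), the number and percent of subjects, and events per subject-year of exposure. State which period takes an event that starts on the roll-over date.

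Split on the actual roll-over date rather than on the analysis windows: in SAP Table 1 the end-of-study window and the protocol Week 72 window both begin after Day 406.

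Two optional additions would help. One is a descriptive table of pre-dose AEs, without a drug-discontinuation category and labelled as imprecise (about 2 to 3 subject-years). The other is a sentence in SAP 3.1.1 saying that discontinuations by reason are shown separately for the main study and the extension.

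The cost is SAP wording and a few more tables, built from AE onset and dosing dates already collected. The downside is that period rates from 14 subjects will be imprecise and should be presented as descriptive.

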### Nature and Extent of the Burden and Risks Associated with Participation, Benefit and

**Group Relatedness:** Participation in this study does not mean that the clinical symptoms, progression of disease, or underlying cause of FSHD1 will be improved or cured. While losmapimod is a potential disease-modifying treatment of FSHD based on its strong preclinical efficacy at inhibiting DUX4 expression and reducing DUX4-regulated gene transcripts and apoptosis across multiple FSHD1 and FSHD2 cell lines without impacting myotube differentiation, benefits of the treatment are not certain. FSHD1 clinical symptoms and/or progression may worsen at any time during this study.

Subjects may experience side effects or complications from the study treatment, as well as AEs and discomforts from the study assessments. Side effects of the investigational product include headache, fatigue, nasopharyngitis, dizziness, and back pain. Side effects of the study assessments include pain or bruising from blood draws; pain, bruising, swelling, redness, or bleeding from muscle biopsy; claustrophobia from MRI; and skin irritation from ECG electrode stickers. All potential side effects will be listed in the subject informed consent form.

Subjects will be asked to follow strict study procedures and respond to questionnaires. There

may also be incidental findings about the subject's health during the study. The subject and his/her primary care physician will be notified if findings are pertinent to his/her health so that appropriate follow-up can be arranged.

There are currently no expected safety risks of the study drug. However, there are some potential safety signals that continue to be investigated. These are summarised in the Investigator's Brochure (IB).

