### **6.4 Summary of Known and Potential Risks and Benefits**

#### **6.4.1 Known and Potential Risks**

There are no known contraindications to the administration of losmapimod.

Losmapimod should not be administered to subjects who are hypersensitive to losmapimod or the excipients used in the losmapimod tablets.

Losmapimod should not be administered to pregnant women or women at risk of becoming pregnant because it was associated with embryo-foetal malformations in rats and rabbits.

Abnormal elevation of transaminases with or without increased bilirubin has been observed with other p38 $\alpha$  inhibitors. Although there is little evidence that this occurs with losmapimod based on the experience from previous clinical trials in over 3,500 subjects, monitoring for potential liver enzyme abnormalities is specified in the protocol as part of safety monitoring.

Clinical studies to date have not shown any consistent increase in the incidence, severity, or type of infections in subjects who received losmapimod compared to placebo. However, because of a potential modest impact of losmapimod on immune function due to inhibition of p38 $\alpha$  pharmacology, there could be circumstances when the theoretical risk of losmapimod administration may outweigh its potential benefits to subjects with FSHD1 (eg, concurrent administration with cytotoxic chemotherapy for cancer). Whether losmapimod could decrease the efficacy of immunisations has not been formally studied.

There has been no increase in renal insufficiency or renal adverse events with losmapimod

compared to placebo in previous clinical trials. However, a small increase in serum creatinine (ratio: 1.07; 95% CI, 1.02 to 1.11) was noted in 1 study, and similar trends were observed in other studies. This increase appears to attenuate with continued treatment and is reversible upon discontinuation. Losmapimod is an inhibitor of MATE1 renal transporter, which may explain this finding.

There has been no increase in cardiac arrhythmias or ECG abnormalities with losmapimod compared to placebo in the clinical trials.

Although no studies have been conducted to evaluate the potential of losmapimod for abuse and dependence, there is no reason to suspect that this will be the case based on its mechanism of action.

There are currently no identified adverse drug reactions and no expected safety risks of losmapimod that would prevent further clinical development in FSHD1 or any other indication.

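### The SAP's adverse event tables leave out the protocol's count of TEAEs, so repeat events appear only in listings and the frequency of recurrent events such as infections is not summarised

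*SAP*

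**What the plan says.** Protocol 10.2.3, under Adverse Events, commits to two counts: "The number of TEAEs and the number of subjects with at least 1 TEAE will be summarised for the following". It then names three breakdowns: SOC and PT, the same by maximum severity, and the same by maximum relatedness.

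SAP 3.2.2 keeps one of the two: "the incidence of TEAEs will be reported as the number of subjects and their percentages with TEAEs within SOC and PT". Its counting rule is "Subjects will be counted only once within a SOC and PT, even if the subject experienced more than one TEAE". The severity summary in 3.2.2 and the summaries of deaths, SAEs, discontinuations and relatedness in 3.2.2.1 are also numbers and percentages of subjects. No SAP table reports a number of events or an event rate. SAP 3.2.1 derives time on treatment, but the adverse event tables do not use it. SAP section 5, on major changes, lists only COVID-19-related changes in how FSHD-RODS, FSHD-HI and MRI results are presented.

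Individual events are kept: "All AEs, treatment emergent or otherwise, will be presented in subject data listings".

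On infection, Protocol 6.4.1 raises a theoretical concern "because of a potential modest impact of losmapimod on immune function", but also says: "Clinical studies to date have not shown any consistent increase in the incidence, severity, or type of infections". The Protocol Summary lists one infection among possible side effects, without a rate: "Side effects of the investigational product include headache, fatigue, nasopharyngitis, dizziness, and back pain".

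**The concern.** Safety is the primary endpoint of the main study and the only endpoint of the extension, and the SAP's visit windows run to a scheduled Day 1876. Protocol 9.5 provides for no data safety monitoring board. The adverse event tables are therefore a main output of the long-term part of the study.

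A count of subjects ever affected answers whether an event occurred, not how often. Infections recur. In the row for a given PT, a subject with one episode and a subject with ten of the same severity contribute identically, and the SOC row discards every infection after the first. The longer the follow-up, the closer a common category moves towards its ceiling and the less the percentage can vary. The protocol's second count would have preserved that information.

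**Working it through.** **Side by side**

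| Item | Protocol 10.2.3 | SAP 3.2.2 and 3.2.2.1 |
|---|---|---|
| Subjects with at least one TEAE | Yes | Yes |
| Number of TEAEs | Yes | No |
| SOC/PT, severity, relatedness | Both counts | Subjects only |
| Change listed in SAP section 5 | – | No |

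The mismatch is textual and depends on no assumed rate.

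**Size: inputs.** N = 14 (Protocol 4.1). Main-study treatment is about 52 weeks (Protocol 3.1.5), so T = 364/365.25 = 1.00 year. The last scheduled visit window is Day 1876 (SAP Table 1), so T = 1876/365.25 = 5.14 years. The documents state no infection rate, so there is no planned figure to reproduce and every rate below is an assumption. All 14 subjects are assumed to be followed throughout.

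**Formulas.** With a constant rate r per person-year and the same risk in every subject, P(at least one event) = 1 − exp(−rT), and expected events = 14 × r × T.

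Worked case, T = 5.14:
- r = 0.5: rT = 2.57, P = 1 − exp(−2.57) = 92%, or 12.9 of 14 subjects; 36 events.
- r = 1.0: rT = 5.14, P = 1 − exp(−5.14) = 99%, or 13.9 of 14 subjects; 72 events.

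A round 5 years gives the same rounded percentages, and 35 versus 70 events.

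| Follow-up | Rate, then doubled | Ever affected | Subjects of 14 | Expected events |
|---|---|---|---|---|
| 5.14 y | 0.05, 0.1 | 23%, 40% | 3.2, 5.6 | 3.6, 7.2 |
| 5.14 y | 0.1, 0.2 | 40%, 64% | 5.6, 9.0 | 7.2, 14.4 |
| 5.14 y | 0.2, 0.4 | 64%, 87% | 9.0, 12.2 | 14.4, 28.8 |
| 5.14 y | 0.5, 1.0 | 92%, 99% | 12.9, 13.9 | 36, 72 |
| 5.14 y | 1.0, 2.0 | 99.4%, 100% | 13.9, 14.0 | 72, 144 |
| 1.00 y | 0.5, 1.0 | 39%, 63% | 5.5, 8.8 | 7, 14 |
| 1.00 y | 1.0, 2.0 | 63%, 86% | 8.8, 12.1 | 14, 28 |

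**Sensitivity to unequal risk.** With gamma frailty of variance 1, P = 1 − 1/(1 + rT). At 5.14 years, r = 0.5 gives 1 − 1/3.57 = 72%, and r = 1.0 gives 1 − 1/6.14 = 84%. The ceiling is then much less of a problem.

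**Reading.** Expected events double when the rate doubles, in every row. The percentage ever affected moves visibly at low rates or over one year, and hardly at all at about 0.5 per person-year or more over about 5 years with homogeneous risk.

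**The case against.** A reader might infer that infections will saturate near 100% and that a doubled infection rate could not be seen. The documents do not support that, for five reasons.

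- **No rate is given.** Saturation needs a pooled rate of about 0.5 per person-year or more over about 5 years with similar risk across subjects. Rarer categories, unequal risk, one-year follow-up, or withdrawal from an optional extension all weaken it.
- **Nothing is hidden.** Every adverse event is listed, and repeats in 14 subjects can be counted by hand. What is missing is the tabulated summary.
- **The counting rule is per SOC and per PT.** A subject with several different infections still appears in each PT row, and the severity table separates subjects by their worst grade. The loss is confined to repeats of the same PT and repeats within the SOC row.
- **There is no comparator.** The study has one arm and no hypothesis testing, so a doubling has no reference in either metric. A raw event count also needs person-time before it can be read as a rate.
- **The protocol does not present infection as an established risk.** It calls the immune concern theoretical and reports no consistent increase versus placebo.

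It can also be said that SAP section 5 covers only major changes, and that Protocol 10.1 sends deviations from the planned analyses to the clinical study report. The omission could still be explained there.

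These points limit the consequence. They do not remove the mismatch: the protocol promised a tabulated number of TEAEs, the SAP contains none, and a listing is not a summary.

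**Conclusion.** The point holds as an unacknowledged departure of the SAP from Protocol 10.2.3 that affects the primary safety summary. It should be corrected, but it does not put the underlying safety data at risk.

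The size depends on the true event rate, which is unknown. Under the assumptions of 14 subjects all followed to Day 1876 and homogeneous Poisson risk, the percentage ever affected is nearly flat at the higher assumed rates (92% versus 99% at 0.5 versus 1.0 per person-year, against 36 versus 72 events). It remains informative at the lower ones (40% versus 64% at 0.1 versus 0.2). The case for the event count does not rest on saturation: the protocol asks for it, and it keeps the repeat events that the subject count drops. The documents do not support a claim that an increase in infections is likely, or that one would go undetected.

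**What to change.** In SAP 3.2.2 and 3.2.2.1, restore the number of TEAEs beside the number and percentage of subjects in the SOC/PT, maximum severity and relatedness tables. If the omission was deliberate, state and justify it in SAP section 5 instead.

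At least for SOC Infections and infestations, add a descriptive number of events per person-year of exposure, with time on treatment from SAP 3.2.1 as the denominator. TEAEs are counted up to 7 days after the last dose, so the SAP should state whether those days are included. The effect is small: 7/1876 = 0.4% of the longest exposure and 7/364 = 1.9% of the main study. No model-based interval is required; with 14 subjects, intervals that allow for clustering would be unreliable, and the study is descriptive.

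The cost is SAP wording, one extra column and one rate line from data already collected, and slightly longer tables. Nothing about study conduct or treatment changes.
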